7.0 Study Withdrawal/Discontinuation

The patient can withdraw from the study at any time by contacting the research team or acute pain anesthesia resident.

8.0 Statistical Considerations

Primary outcome: VAS score at 24 and 48 hours

Primary Research Hypothesis: ESP will provide lower pain scores compared to surgeon infiltration and ESP with LB will provide longer pain control than ESP with SB.

Secondary outcomes: Opioid usage after 1, 24, 48 and 72 hours. Pain scores using VAS at rest and on movement at 1, 24, 48 and 72 hours. Patient satisfaction scores at 24 and 48 hours. Nausea

scores at 1, 24, 48 and 72 hours. Sedation scores at 1, 24, 48 and 72 hours. Time to first bowel movement, incidence of urinary retention, and incidence of respiratory depression will be recorded as well.

Secondary Research Hypotheses: ESP blocks will show improved pain control, improved patient satisfaction scores, and decreased nausea and sedation scores compared to surgeon infiltration. Statistical analysis will be performed using a standard statistical program (SAS or SPSS). All data will be summarized (means, standard deviations, standard errors, and ranges for continuous variables; frequencies and percentages for categorical variables) by group. Demographic data will be compared between the three groups using ANOVA or chi-square tests as appropriate. The primary outcome, VAS at 24 and 48 hours, will be compared between the groups using repeated measures ANOVA; the model will include fixed effects for group, time, and the group by time interaction and random effects to allow correlations between the two times and different variances for the two times. Pain and satisfaction scores and opioid usage over time will be analyzed using repeated measures ANOVA. Nausea and sedation scores will be compared between groups at each time point using Mantel-Haenszel chi-square tests for ordered categorical data. Distributions of the continuous variables will be examined, and a transformation of the data (e.g. natural logarithm) or nonparametric tests will be used as necessary. A 5% significance level will be used for all comparisons.

Based on prior studies, the coefficient of variation for the VAS score at 24 and 48 hours is estimated to be 0.70. With a sample size of 40 per group, the study will have 91% power be able to detect a 60% decrease in VAS score between any two groups, assuming two-sided tests each conducted at a 5% significance level.

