3.0 Inclusion/Exclusion Criteria

Inclusion criteria:

- Pt undergoing VATS including but not limited to wedge or lobectomy at Indiana University Hospital,
- ASA 1,2,3 or 4
- Age 18 or older, male or female
- Desires regional anesthesia for postoperative pain control

Exclusion criteria:

- Any contraindication for Erector Spinae Plane block
- History of substance abuse in the past 6 months which would include heroin, marijuana or any other illegal street drugs
- Patient staying intubated after surgery
- Patient (home dose) taking more than 30mg PO morphine equivalent per day
- Known allergy or other contraindications to the study medications, which include dilaudid and bupivacaine.

- Pts. scheduled for a pleurodesis, decortication or esophagectomy at Indiana University Hospital
- BMI greater than 40.0.

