4.0 Enrollment/Randomization

All VATS cases scheduled by thoracic surgeons at IU Health University Hospital will be identified. The subjects will be contacted initially face-to-face by either [name] or [name] in their clinics prior to their scheduled surgery date. They will be given a copy of the consent and authorization form explaining this study. The subjects will again be contacted face to face in POCU on the day of surgery and the study will be explained in detail and all questions will be answered. If participation is agreed, written consent will be taken and a signed copy of both the authorization and consent will be given to the participant.

A total of 120 subjects will be randomized by the computer program Research Randomizer into three groups (40 per group): The primary investigator will inform the anesthesiologist who will be doing the block as to what group the patients are randomized to. The research staff completing the patients assessments will be the only person blinded to the randomization.

- 1. Ultrasound guided LB Erector Spinae Plane Block with 20ml of Exparel® and 10ml 0.25% bupivacaine
- 2. Ultrasound guided SB Erector Spinae Plane Block with 30ml 0.5% bupivacaine
- 3. Surgeon Infiltration under video guidance with 20ml of Exparel® and 10ml of 0.25% bupivacaine

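### The primary VAS model adjusts for no pre-treatment factor and randomisation is not stratified; a short prespecified covariate list would be a cheap, modest and conditional gain in precision

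*Combined protocol and SAP*

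**What the plan says.** Section 8.0 (Statistical Considerations) defines the endpoint as "Primary outcome: VAS score at 24 and 48 hours" and analyses it by repeated measures ANOVA, in which "the model will include fixed effects for group, time, and the group by time interaction". The rest of the model is "random effects to allow correlations between the two times and different variances for the two times". That part describes the covariance of the two measurements and adjusts for nothing measured before treatment.

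The only between-group use of baseline data is this: "Demographic data will be compared between the three groups using ANOVA or chi-square tests as appropriate". Nothing follows from the result of those tests.

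Section 4.0 (Enrollment/Randomization) states: "A total of 120 subjects will be randomized by the computer program Research Randomizer into three groups (40 per group"). It names no stratification factor.

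Section 3.0 (Inclusion/Exclusion Criteria) sets the spread of patients:
- Procedures are open-ended: "Pt undergoing VATS including but not limited to wedge or lobectomy at Indiana University Hospital". One exclusion narrows this: "Pts. scheduled for a pleurodesis, decortication or esophagectomy at Indiana University Hospital".
- Any adult age and ASA class 1 to 4 are eligible.
- Home opioid use is capped, because this group is excluded: "Patient (home dose) taking more than 30mg PO morphine equivalent per day".

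**The concern.** Neither the design nor the analysis uses what is known about a patient before treatment. Procedure, age and home opioid use plausibly predict postoperative pain. The protocol itself treats them as relevant: it excludes three procedures, caps home opioids, and varies the gabapentin premedication by age (section 5.0). Scheduled procedure and home opioid dose must be ascertained to apply the eligibility criteria, so the information should exist before treatment.

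If these factors explain a share R² of the within-group VAS variance, the unadjusted model leaves that share in the residual. Confidence intervals are then wider than they need be. At stake is the precision of the three pairwise contrasts with 40 patients per arm. It matters most for the liposomal versus standard bupivacaine contrast, where section 1.0 acknowledges conflicting evidence and the true difference may be smaller than the one used for power.

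**Working it through.** **Inputs from the plan.** 40 per group, 120 in total (section 4.0). CV 0.70, two-sided 5% level, stated power 91% for a 60% decrease (section 8.0).

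**Inputs assumed.** R² is not in the documents; 5%, 10%, 20% and 30% are used. Four extra parameters are counted: procedure in three classes (2), age (1), home opioid none/any (1).

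**Step 1: the plan's own figure.** Two-sample power by noncentral t, 78 degrees of freedom, noncentrality d × √(40/2).
- Literal 60% decrease, raw scale, SD = 0.70 × control mean: d = 0.60/0.70 = 0.857, power 96.6%.
- Literal 60% decrease, log scale: log SD = √ln(1 + 0.70²) = 0.6315, d = |ln 0.40|/0.6315 = 1.451, power above 99.9%.
- Ratio of 1.6 between groups, log scale: d = ln(1.6)/0.6315 = 0.4700/0.6315 = 0.744, power 90.8% (91.4% by normal approximation).

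The 91% does not come back from a literal 60% decrease. It does from a ratio of 1.6, which is a 37.5% decrease (1 − 1/1.6). That reading is the base below. The mismatch in the power statement is a separate matter.

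**Step 2: gain and cost of adjustment.** Adjustment multiplies the residual variance by (1 − R²). Estimating q covariate parameters inflates the variance of a contrast by about 1 + q/(120 − 3 − q − 1). For q = 4 this is 1 + 4/112 = 1.036, or 3.6%. Hence

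d(net) = d / √[(1 − R²) × 1.036], and effective n per group = 40 / [(1 − R²) × 1.036].

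| Assumed R² | Net power, base 90.8% (d = 0.744) | Net power, base 80% (d = 0.634) | Effective n per group, net |
|---|---|---|---|
| No adjustment | 90.8% | 80.0% | 40 |
| 5% | 91.2% | 80.6% | 40.7 |
| 10% | 92.6% | 82.6% | 42.9 |
| 20% | 95.1% | 86.8% | 48.3 |
| 30% | 97.1% | 90.8% | 55.2 |

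The 80% column is illustrative. It shows a smaller effect than the plan's, because precision is worth more there.

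**Step 3: break-even.** Gain and cost cancel when (1 − R²) × 1.036 = 1, that is R² = 1 − 1/1.036, about 3.4%. At R² = 2%, power falls from 90.8% to about 90.4%, and from 80.0% to about 79.4%.

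**The case against.** The strongest reply is that nothing here is an error. With randomised allocation the unadjusted contrast is unbiased and holds its type I error. That stands, and it sets the weight of the point.

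A reader might go further and infer that a chance imbalance in procedure type distorts the result. With an assumed 50:50 wedge/lobectomy mix, two given arms differ by 15 percentage points or more in about 22% of randomisations, and by 20 or more in about 9%. The documents do not support that reading:
- The mix is not given, and 50:50 is the worst case. At 20:80 the figures fall to about 12% and 4%.
- The standard error already allows for such imbalance. If procedure explained 10% of the variance in a 50:50 mix, the two classes would differ by √0.10/0.5 = 0.632 SD. A 15-point imbalance would then shift the contrast by 0.15 × 0.632 = 0.095 SD. Against a standard error of √(2/40) = 0.224 SD, that is 0.42 standard errors.

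It is also fair to say that the opioid cap and the excluded procedures narrow the spread, so R² may be small. Nor do the documents establish that the covariates are stored as analysis variables. Section 8.0 does not define demographic data, and section 3.0 needs only a check of home dose against a threshold. Finally, section 8.0 allows nonparametric tests if distributions require them, and covariate adjustment does not carry over to those directly. All three limits stand.

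**Conclusion.** The point holds as a cheap improvement. The primary model omits every pre-treatment factor, the randomisation does not balance them, and whatever VAS variance they explain is left in the residual. From the plan's own power level the net gain is about 0.4 points at R² = 5%, 1.8 at 10%, 4.3 at 20% and 6.3 at 30%. For an effect with 80% power it is about 0.6, 2.6, 6.8 and 10.8 points. Below an R² of about 3-4% there is a slight loss.

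These sizes rest on an assumed R², on four parameters, and on reading the sample-size statement as a ratio of 1.6. If the literal 60% decrease on the raw scale is meant, power is already 96.6% and there is less to gain.

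The omission does not make the planned comparison biased or invalid. Dropping the demographic significance tests would not change the primary result. Adjusting for a baseline pain score is not available either, because section 5.0 schedules the first VAS at 1 hour.

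**What to change.** In section 8.0, before anyone reviews outcome data:

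1. Add to the primary VAS model, as fixed effects: planned procedure class (wedge / lobectomy / other), age, and preoperative home opioid use (none / any). Use the planned procedure, not the one performed, since only the former is fixed before treatment.
2. Use the same list in the opioid-usage model. Section 8.0 now calls it only a repeated measures ANOVA, so its terms need to be written out.
3. Keep the unadjusted model as a sensitivity analysis.
4. State that the 1-hour VAS is not a covariate, because it is measured after treatment.
5. Confirm that the three covariates are recorded in the study database, and add fields if they are not.
6. Say what happens to the adjustment if the nonparametric fallback is used.

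The cost is a few sentences, possibly two or three database fields, and about 3.6% variance inflation. No extra patients or visits are needed.

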5.0 Study Procedures

All the erector spinae plane blocks will be placed preoperatively after sedation, before intubation and prior to surgery. All procedures will be done using sterile technique with masks, hats, and sterile gloves. All procedures will be placed under the supervision of the attending anesthesiologist on the acute pain service or the attending anesthesiologist in the VATS room.

To perform the ESP block, an ultrasound probe is used to visualize the ES musculature about 3 cm laterally from the T5 spinous process. In a cephalad-to-caudad direction advance the needle and inject the anesthetic in the interfacial plane deep to the ES muscles. Confirm positioning by visualization of needle tip and elevation of ES muscles off the transverse process with anesthetic injection. Surgeon infiltration is performed intraoperatively under direct thoracoscopic guidance. The intercostal space will be visualized and injected with LB. Typically, T4 through T8 are infiltrated with 2-3mL of the anesthetic mixture.

All patients will receive 1gm of acetaminophen and 600mg of gabapentin preoperatively. Patients above 70yo will receive 300mg of gabapentin. General anesthesia will be induced in the operating room and the patient will be placed in the lateral position for the VATS procedure. All patients will

receive intraoperative lidocaine and ketamine which is used to decrease opioid use after surgery and is being used as part of ERAS protocol. The patients will be intubated with dual lumen endotracheal tubes and placed on one-lung ventilation for the procedure. All patients will receive intravenous patient-controlled analgesia (PCA hydromorphone) post-operatively for breakthrough pain. They will also be scheduled on PO acetaminophen. PO oxycodone PRN will be started on POD 1 once patients tolerate diet.

Opioid usage at 1,24,48,72 hours after the block will be recorded by a member of the research team. Pain scores at rest and on movement (knee flexion) will be measured by the investigator using Visual Analog Scale (VAS). Nausea will be measured using a categorical scoring system (none=0; mild=1; moderate=2; severe=3). Sedation scores will also be assessed by a member of the study team using a sedation scale (awake and alert=0; quietly awake=1; asleep but easily roused=2; deep sleep=3). All these parameters will be measured at 1, 24, 48 and 72 hours after the epidural or PVB. Patients will be encouraged to ambulate on postoperative day 1 under supervision.

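### Section 8 does not say which Mantel-Haenszel test will compare nausea and sedation; if it is the usual 1-df form run across three unordered arms, the result depends on how the arms are numbered

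*Combined protocol and SAP*

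**What the plan says.** Section 4.0 sets up three arms of equal size: "A total of 120 subjects will be randomized by the computer program Research Randomizer into three groups (40 per group"). They are listed as 1, "Ultrasound guided LB Erector Spinae Plane Block"; 2, "Ultrasound guided SB Erector Spinae Plane Block"; and 3, "Surgeon Infiltration under video guidance". The arms differ in technique, in drug, or in both. The document does not rank them for nausea or sedation, and it does not say that the list numbers are analysis codes.

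Section 5.0 gives both outcomes four ordered levels. For nausea: "Nausea will be measured using a categorical scoring system (none=0; mild=1; moderate=2; severe=3"). For sedation: "awake and alert=0; quietly awake=1; asleep but easily roused=2; deep sleep=3". Both are recorded at 1, 24, 48 and 72 hours.

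Section 8.0 gives the analysis in one sentence: "Nausea and sedation scores will be compared between groups at each time point using Mantel-Haenszel chi-square tests for ordered categorical data". Degrees of freedom, arm scores and the set of comparisons are not given. The secondary hypothesis in the same section is that the ESP blocks lower nausea and sedation relative to surgeon infiltration. The software is SAS or SPSS, and every comparison is made at the 5% level.

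**The concern.** In SAS the line labelled Mantel-Haenszel chi-square, and in SPSS the equivalent linear-by-linear association, is (N-1)r² on 1 df, where r is the correlation between the outcome score and the numeric arm code. With two arms the coding is immaterial. With three unordered arms it is not: the test looks for a straight-line trend across whatever numbers the arms were given.

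An analyst who follows the sentence literally could report that line for each of the 2 scores × 4 times = 8 planned comparisons. A finding of no difference could then be an artefact of numbering, and renumbering the arms could change it. Leaving the variant and the codes open until the data are seen also leaves room for choice on the same table.

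**Working it through.** **Inputs from the document.** Three arms of 40, so N = 120; scores 0 to 3; 5% level. The plan gives no power figure and no score distribution for nausea or sedation, so there is no stated figure to reproduce, and every distribution below is an assumption.

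**Formulas.** Let n = 40, let ȳ₁, ȳ₂, ȳ₃ be the arm means, ȳ the overall mean, and SST the total sum of squares about ȳ.

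- 1-df statistic with codes 1, 2, 3 (equivalently -1, 0, 1): Q₁ = (N-1)·[n(ȳ₃ - ȳ₁)]² / (2n·SST). The mean of the middle-coded arm does not enter the numerator. This is algebra and rests on no assumed distribution.
- 2-df row-mean-scores statistic: Q₂ = n·Σ(ȳ_g - ȳ)² / [SST/(N-1)]. Arm codes do not appear.

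**A fixed example (invented counts).** Two arms have 22/10/6/2 patients at scores 0/1/2/3 and one arm has 10/12/12/6.

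- Means: 28/40 = 0.70 and 54/40 = 1.35. Overall mean: (28 + 28 + 54)/120 = 0.9167.
- Sum of squared scores: 52 + 52 + 114 = 218. SST = 218 - 110²/120 = 117.17.
- Differing arm coded at an end: Q₁ = 119 × (40 × 0.65)² / (80 × 117.17) = 8.58, p = 0.003.
- Differing arm coded in the middle: the end arms have equal means, so Q₁ = 0.00, p = 1.00.
- Either coding: Q₂ = 40 × (2 × 0.2167² + 0.4333²) / (117.17/119) = 11.44, p = 0.003.
- Two arms only (one of each kind, N = 80): both statistics equal 8.15, so coding does not matter in a pairwise test.

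**Power by simulation, 40 per arm.** Set A: reference probabilities 45/30/17/8% and an odds ratio of 3 (20,000 trials). Set B: 55/25/15/5% (mean 0.70) against 25/30/30/15% (mean 1.35) (40,000 trials). Each cell is 1-df against 2-df.

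| Pattern and coding | Set A | Set B |
|---|---|---|
| No difference | about 5% v 5% | about 5% v 5% |
| Only ESP-SB differs, codes as listed | 3-6% v 66-79% | 3% v 87% |
| Both ESP arms better, codes as listed | 68% v 70% | 85% v 88% |
| Both ESP arms better, infiltration given the middle code | about 3% v 70% | 3% v 88% |
| Graded LB < SB < infiltration, codes as listed | 66% v 55% | 84% v 75% |

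The Set A range in the second row covers ESP-SB better and ESP-SB worse than the other two arms. When both ESP arms are better, a 1-df contrast of the two ESP arms together against infiltration has about 80% power in Set A and 93% in Set B, above both tests in the table. If only one ESP arm differs, that contrast falls to about 40% in Set B.

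**The case against.** A reader might infer that the plan has chosen a wrong test and will test nausea and sedation against the wrong alternative. The document does not support that. The sentence fixes no degrees of freedom and does not say that all three arms enter one test. Two-arm Mantel-Haenszel tests fit the wording, and the hypothesis for these outcomes is itself a two-group comparison. The row-mean-scores form also belongs to the Mantel-Haenszel family for ordered responses. Both are free of the problem.

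The severe power losses also need particular conditions. One needs ESP-SB to differ while ESP-LB matches infiltration, a pattern that no hypothesis in the plan predicts. The other needs infiltration to take the middle code, although Section 4.0 lists it third. For the hypothesised pattern in the listed order, little is lost.

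Nor is the 2-df test better in every case. If the effect is graded, the 1-df test in the listed order is the stronger one. Such a gradient is plausible, since the plan expects ESP to beat infiltration on pain and LB to outlast SB.

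All of this stands, and it limits the point to a conditional one. It does not remove it. The sentence names no pairs, no 2-df form and no arm scores, the default output line is the code-dependent one, and the plan states no gradient for nausea or sedation that would justify a trend test.

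**Conclusion.** The point holds as an under-specified analysis with a conditional risk. If the 1-df correlation form is run once across the three arms, its result depends on arbitrary codes, and a difference confined to the middle-coded arm is detected with about 3-6% power where a 2-df test has 66-79%. In the listed order the hypothesised pattern loses only about 2 percentage points (68% against 70%), but a direct contrast would gain about 12 (80% against 68%).

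The dependence on codes is algebraic. The sizes rest on the assumed score distributions and an odds ratio of 3; Set B gives the same picture at higher power. A reader should not infer inflated false-positive rates, since both tests reject about 5% of the time under the null. The primary analysis of VAS is untouched. The point is worth correcting but does not threaten the trial's main conclusion.

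**What to change.** Amend the one sentence in Section 8.0 to state, for each time point, either or both of the following:

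- for the three-arm comparison, the Cochran-Mantel-Haenszel row-mean-scores test (2 df, arm nominal, score ordinal);
- Mantel-Haenszel tests on named two-group contrasts: ESP versus infiltration, as the secondary hypothesis states, and the individual pairs if they are wanted.

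Naming both is sensible. The ESP-versus-infiltration contrast answers the stated hypothesis, and the 2-df test covers the case where only one ESP arm differs.

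No extra patients, data or special software are needed. There are two costs. The 2-df test gives up some power if the effect is truly graded LB < SB < infiltration (about 55% against 66% in Set A, 75% against 84% in Set B). Testing all three pairs would mean 3 × 8 = 24 tests, each at 5%, so the plan should say which of them are descriptive. If the investigators do expect a graded effect on nausea or sedation, they can keep the trend test, provided that the ordering and the arm scores are written down before the data are examined.

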9.0 Privacy/Confidentiality Issues

All study papers containing patient identifiers will be kept in each subjects confidential study file accessible to only the research team. All records will be kept in a locked room in a locked cabinet that only authorized staff enters. Collected data from each enrolled participant will be recorded on Redcap which is a secure web-based data collection tool. Three years after completion of the study, all electronic information and paperwork containing patient identifiers will be deleted or shredded.

